APPENDIX B. TABLE SHELLS

Table 1A: Eligibility Criteria June 2015 to December 2021 (Komodo Health Only)

	All Patients
	$\mathbf{N} - \mathbf{A}\mathbf{A}$
Eligibility Criteria	n (%)
All patients with PBC code	
PBC diagnosis	
1 inpatient claim	
2 outpatient claims	
1 inpatient and/or 2 outpatient claims	
PBC Dx + Laboratory data	
ALP	
Bilirubin	
AST	
ALT	
ALP and Bilirubin and AST and ALT	
PBC Dx + Labs + Prescription record for UDCA	
PBC Dx + Labs + UDCA failure	
UDCA intolerant	
Inadequate UDCA response	
PBC Dx + Labs + UDCA failure + 12 months data before UDCA failure	
PBC Dx + Labs + UDCA failure + 12 months pre-index data + 12 months closed claims	
PBC Dx + Labs + UDCA failure + 12 months pre-index data + 12 months closed claims + OCA	

Table 1B: Eligibility Criteria June 2015 to December 2021 (Global PBC Registry Only)

	All Patients
	N = XX
Eligibility Criteria	n (%)
All patients with PBC diagnosis	
PBC Dx + Laboratory data	
ALP	
Bilirubin	
AST	
ALT	
ALP and Bilirubin and AST and ALT	
PBC Dx + Labs + Prescription record for UDCA	
PBC Dx + Labs + UDCA failure	
UDCA intolerant	
Inadequate UDCA response	
PBC Dx + Labs + UDCA failure + 12 months data before UDCA failure	
PBC Dx + Labs + UDCA failure + 12 months pre-index data + OCA	

Table 2:Sex of All Eligible Patients by Year

All Eligible Patients							
	2016 N=X	2017 N=X	2018 N=X	2019 N=X	2020 N=X	2021 N=X	Overall N=X
Sex	n (%)						
Female							
Male							
Missing							

Table 3:Age of All Eligible Patients by Year

	All Eligible Patients						
	2016	2017	2018	2019	2020	2021	Overall
Age	N=X	N=X	N=X	N=X	N=X	N=X	N=X
Valid, n (%)							
Missing, n (%)							
Mean (SD)							
Skewness							
Median							
(Q1, Q3)							
Range							

	All Eligible Patients									
	2016	2017	2018	2019	2020	2021	Overall			
	N=X	N=X	N=X	N=X	N=X	N=X	N=X			
Race	n (%)	n (%)	n (%)	n (%)	n (%)	n (%)	n (%)			
White										
Black or African American										
Asian, Native Hawaiian or other Pacific Islander										
American Indian or Alaskan Native										
Other										
Missing										
* Note that race is not sys	stematicall	v reported	l in either	database.	and thus is	s only avai	lable on a s			

Table 4: **Race of All Eligible Patients by Year***

Note that race is not systematically reported in either database, and thus is only available on a subset of patients.

Table 5A: **Region by Year (Komodo Health Only)**

	All Eligible Patients									
	2016 N=X	2017 N=X	2018 N=X	2019 N=X	2020 N=X	2021 N=X	Overall N=X			
Region	n (%)	n (%)	n (%)	n (%)	n (%)	n (%)	n (%)			
Northeast										
Midwest										
West										
South										
Missing, n (%)										
	All Eligible Patients									
-----------------	-----------------------	-------	-------	-------	-------	-------	---------	--		
	2016	2017	2018	2019	2020	2021	Overall			
	N=X	N=X	N=X	N=X	N=X	N=X	N=X			
Country	n (%)	n (%)	n (%)	n (%)	n (%)	n (%)	n (%)			
The Netherlands										
UK										
Belgium										
Germany										
France										
Italy										
Spain										
Greece										
Canada										
USA										
Argentina										
Israel										
Japan										
China										

Table 5B: Patients by Country and by Year (Global PBC Registry Only)

Table 6:Index Hepatic Laboratory Values by Year (TB, ALP, ALT, AST)	
---	--

	All Eligible Patients							
Laboratory Value Statistic	2016 N pts=X N index =X	2017 N pts=X N index =X	2018 N pts=X N index =X	2019 N pts=X N index =X	2020 N pts=X N index =X	2021 N pts=X N index =X	Overall N pts=X N index =X	
ТВ								
Valid, n (%)								
Missing, n (%)								
Mean (SD)								
Skewness								
Median								
(Q1, Q3)								
Range								
ALP								
Valid, n (%)								
Missing, n (%)								
Mean (SD)								
Skewness								
Median								
(Q1, Q3)								
Range								
ALT								
Valid, n (%)								
Missing, n (%)								
Mean (SD)								
Skewness								
Median								
(Q1, Q3)								
Range								
AST		-		-			-	
Valid, n (%)								
Missing, n (%)								
Mean (SD)								
Skewness								
Median								
(Q1, Q3)								
Range								

Table 7:Index Platelet Counts by Year

	All Eligible Patients									
Platelet counts	2016 N pts=X N index =X	2017 N pts=X N index =X	2018 N pts=X N index =X	2019 N pts=X N index =X	2020 N pts=X N index =X	2021 N pts=X N index =X	Overall N pts=X N index =X			
Valid, n (%)										
Missing, n (%)										
Mean (SD)										
Skewness										
Median										
(Q1, Q3)										
Range										

Table 8:On UDCA Treatment by Year

	All Eligible Patients N=X
On UDCA treatment	n (%)
2016	
2017	
2019	
2020	
2021	

Table 9:UDCA Failure by Year

	All Eligible Patients N=X
UDCA failure	n (%)
2016	
2017	
2019	
2020	
2021	

Table 10:Time (Months) Since First UDCA Failure Until the Index Date (inclusive) by
Year

	All Eligible Patients								
Months since UDCA failure until index date	2016 N=X	2017 N=X	2018 N=X	2019 N=X	2020 N=X	2021 N=X	Overall N=X		
Valid, n (%)									
Missing, n (%)									
Mean (SD)									
Skewness									
Median									
(Q1, Q3)									
Range									

Table 11: Clinical Evidence of Portal Hypertension (Platelets <150k; Non-Bleeding Varices; Platelets and/or Non-Bleeding Varices) by Year	All Eligible Patients N=X
Clinical evidence of portal hypertension by year	n (%)
2016	
2017	
2019	
2020	
2021	

Table 12:Cirrhosis by Year

	All Eligible Patients N=X
Cirrhosis by year	n (%)
2016	
2017	
2019	
2020	
2021	

	All Eligible Patients								
Charlson Comorbidity Index Score by year	2016 N=X	2017 N=X	2018 N=X	2019 N=X	2020 N=X	2021 N=X	Overall N=X		
Valid, n (%)									
Missing, n (%)									
Mean (SD)									
Skewness									
Median									
(Q1, Q3)									
Range									

 Table 13:
 Charlson Comorbidity Index Score by Year

Table 14:	Insurance Type a	t Index Date b	v Year (Komodo	Health	Only)
1 abit 17.	insurance i ype a	i much Date D	y i cai (IXUIIIUUU	mann	omy

	All Eligible Patients							
Health Insurance Type on	2016 N=X	2017 N=X	2018 N=X	2019 N=X	2020 N=X	2021 N=X	Overall N=X	
the index date	n (%)	n (%)	n (%)	n (%)	n (%)	n (%)	n (%)	
Commercial								
Self-insured/Exchanges								
Medicare								
Medicaid								
Dual eligible								
Other								
Missing								

	Year						
Patients	2016	2017	2018	2019	2020	2021	Overall
Statistic	N=X						
All Eligible Patients							
Patients with index date							
# index dates/patient with index date							
Mean (SD)							
Skewness							
Median							
(Q1, Q3)							
Range							
Non-OCA		-	-	-			
Patients with index date							
# index dates/patient with index date							
Mean (SD)							
Skewness							
Median							
(Q1, Q3)							
Range							
OCA							
Patients with index date							
# index dates/patient with index date							
Mean (SD)							
Skewness							
Median							
(Q1, Q3)							
Range							

Table 15:Number of Index Dates by Year

 Table 16:
 Sex of Patients by Group before and After Weighting

	Before Weighting		After Weighting	
	Non-OCA-treated	OCA-treated	Non-OCA-treated	OCA-treated
	N patients =	N patients =	N patients =	N patients =
	N index dates =	N index dates =	N index dates =	N index dates =
Sex	n (%)	n (%)	n (%)	n (%)
Female				
Male				

	Before W	eighting	After Weighting	
	Non-OCA-treated	OCA-treated	Non-OCA-treated	OCA-treated
	N patients =	N patients =	N patients =	N patients =
Age	N index dates =			
Mean (SD)				
Skewness				
Median				
(Q1, Q3)				
Range				

Table 17: Age of Patients by Group Before and After Weighting

Table 18A:	Region by Gro	1D Before and After	r Weighting (Ko	modo Health Only)

	Before W	eighting	After Weighting		
	Non-OCA-treated	OCA-treated	Non-OCA-treated	OCA-treated	
	N patients =	N patients =	N patients =	N patients =	
	N index dates =				
Region	n (%)	n (%)	n (%)	n (%)	
Northeast					
Midwest					
West					
South					
Missing					

Table 18B:	Country by Gro	ip Before and Aft	er Weighting (Global PBC Registry	Only)
					,,,,

	Before W	eighting	After Weighting	
	Non-OCA-treated	OCA-treated	Non-OCA-treated	OCA-treated
	N patients =	N patients =	N patients =	N patients =
	N index dates =			
Countries in Global PBC	n (%)	n (%)	n (%)	n (%)

	Before W	eighting	After Weighting		
	Non-OCA-treated	OCA-treated	Non-OCA-treated	OCA-treated	
Hepatic Laboratory Valua	N patients =	N patients =	N patients =	N patients =	
Statistic	N index dates =	N index dates =	N index dates =	N index dates =	
ТВ					
n (%)					
Mean (SD)					
Skewness					
Median					
(Q1, Q3)					
Range					
ALP					
n (%)					
Mean (SD)					
Skewness					
Median					
(Q1, Q3)					
Range					
ALT			1		
n (%)					
Mean (SD)					
Skewness					
Median					
(Q1, Q3)					
Range					
AST					
n (%)					
Mean (SD)					
Skewness					
Median					
(Q1, Q3)					
Range					

Table 19:Hepatic Laboratory Values by Group (TB, ALP, ALT, AST) Before and
After Weighting

	Before Weighting		After Weighting		
	Non-OCA-treated	OCA-treated	Non-OCA-treated	OCA-treated	
	N patients =	N patients =	N patients =	N patients =	
Platelet counts	N index dates =	N index dates =	N index dates =	N index dates =	
n (%)					
Mean (SD)					
Skewness					
Median					
(Q1, Q3)					
Range					

Table 20: Platelet Counts by Group Before and After Weighting

 Table 21:
 Patients on UDCA Treatment by Group Before and After Weighting

	Before W	Veighting	After Weighting	
	Non-OCA-treated OCA-treated		Non-OCA-treated	OCA-treated
	N patients =	N patients =	N patients =	N patients =
	N index dates =	N index dates =	N index dates =	N index dates =
UDCA Treatment	n (%)	n (%)	n (%)	n (%)
Yes				
No				

Table 22:Duration (Months) of Receiving UDCA by Group Before and After
Weighting

	Before Weighting		After Weighting	
	Non-OCA-treated	OCA-treated	Non-OCA-treated	OCA-treated
Duration (in	N patients =	N patients =	N patients =	N patients =
months) of UDCA treatment	N index dates = N index dates =		N index dates =	N index dates =
Mean (SD)				
Skewness				
Median				
(Q1, Q3)				
Range				

Table 23:Time (Months) from UDCA Failure Until the Index Date by Group Before
and After Weighting

	Before Weighting		After Weighting	
	Non-OCA-treated	OCA-treated	Non-OCA-treated	OCA-treated
Time (in months)	N patients =	N patients =	N patients =	N patients =
from UDCA failure until the index date	N index dates = N index dates =		N index dates =	N index dates =
Mean (SD)				
Skewness				
Median				
(Q1, Q3)				
Range				

Table 24:Clinical Evidence of Portal Hypertension (Platelets <150k; Non-Bleeding
Varices; Platelets and/or Non-Bleeding Varices) by Group Before and After
Weighting

	Before W	Veighting	After Weighting		
	Non-OCA-treated	OCA-treated	Non-OCA-treated	OCA-treated	
	N patients =	N patients =	N patients =	N patients =	
Clinical evidence of portal hypertension	N index dates =				
	n (%)	n (%)	n (%)	n (%)	
Yes					
No					

Table 25:	Cirrhosis by	Group Before	and After	Weighting
	•			

	Before W	eighting	After Weighting		
	Non-OCA-treated OCA-treated		Non-OCA-treated	OCA-treated	
	N patients = N patients =		N patients =	N patients =	
	N index dates = N index dates =		N index dates =	N index dates =	
Cirrhosis	n (%)	n (%)	n (%)	n (%)	
Yes					
No					

	Before Weighting			After Weighting					
	Non-OC	A-treated	OCA-treated		Non-OCA-treated		OCA-treated		
Charlson	N patients =		N pat	N patients =		N patients =		N patients =	
Score	morbidity Index ore N index dates = N index dates =		N index dates =		N index dates =				
Mean (SD)									
Skewness									
Median									
(Q1, Q3)									
Range									

Table 26: Charlson Comorbidity Index Score by Group Before and After Weighting

Table 27:Insurance Type at Index Date by Group Before and After Weighting
(Komodo Health Only)

	Before W	eighting	After Weighting		
	Non-OCA-treated	OCA-treated	Non-OCA-treated	OCA-treated	
	N patients =	N patients =	N patients =	N patients =	
.	N index dates =	N index dates =	N index dates =	N index dates =	
index date	n (%)	n (%)	n (%)	n (%)	
Commercial					
Medicare					
Medicaid					
Dual eligible					
Other					
Missing					

Table 28:	Logistic	regression	for Non-	OCA vs	OCA-treated

Parameter	Ν	Estimate	SE
Non-OCA			
OCA			
Gender			
Age			
Region/Country			
Time (in months) since PBC diagnosis			
Calendar year of PBC diagnosis			
Labs			
ALP			
Total bilirubin			
ALT			
AST			
UDCA duration			
Clinical evidence of portal HTN			
Cirrhosis			
Charlson Comorbidity Index Score			
Insurance type			

Table 29:Distribution of Propensity Weights

	Non-OCA-treated	OCA-treated
	N patients =	N patients =
Propensity weights	N index dates =	N index dates =
Mean (SD)		
Skewness		
Median		
(Q1, Q3)		
Range		

Table 30:	Standardized Differences of the Mean Before and After V	Weighting
		· · ·

	Standardized Mean Difference		
Parameter	Unweighted	Weighted	
Gender			
Age			
Region/Country			
Time (in months) since PBC diagnosis			
Calendar year of PBC diagnosis			
ALP			
Total bilirubin			
ALT			
AST			
UDCA duration			
Clinical evidence of portal HTN			
Cirrhosis			
Charlson Comorbidity Index Score			
Insurance type			

Table 31:Results Unadjusted, Adjusted and Weighted Cox Regression on Time to
Composite Event

Parameter	n	HR	95% CI	p-value
Unique cases				
Unique persons				
Cases				
Person trials				
Unadjusted				
Adjusted for baseline covariates				
Weighted				

Figure 1: Adherence to OCA Treatment over Time

Figure 2A: Eligible Patients by Number of Trials

Figure 2B: Eligible Control Patients by Number of Trials

Figure 2C: Eligible OCA-treated Patients by Number of Trials

Figure 3A: Distribution of Propensity Scores: Unweighted

Figure 3B: Distribution of Propensity Scores: Weighted

Figure 4: Kaplan-Meier Survival Curve: Composite Event-free Survival by Treatment Arm

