The only approved drug therapy for PBC has been the bile acid ursodeoxycholic acid (UDCA), a physiological constituent of human bile (Lindor 2009). While UDCA therapy had a marked effect on the treatment of PBC, up to 40% of patients showed a suboptimal response or no response to UDCA (Corpechot 2008, Kumagi 2010). Such patients were at significantly increased risk of a poor clinical outcome due to PBC disease progression. Obeticholic acid (OCA) is a farnesoid X receptor (FXR) agonist and a modified bile acid that is derived from the primary bile acid chenodeoxycholic acid (CDCA), the natural human FXR ligand. OCA (Ocaliva[®]) has received marketing authorization in the US, the European Union (EU), and several other countries for the treatment of PBC in combination with UDCA in adults with an inadequate response to UDCA or as monotherapy in adults unable to tolerate UDCA. In the US, Ocaliva is contraindicated in patients with decompensated cirrhosis (eg, Child-Pugh Class B or C), a prior decompensation event, complete biliary obstruction, or compensated cirrhosis with evidence of portal hypertension. Approval in the US and the EU was based on a surrogate endpoint (reduction in ALP), and as part of regulatory commitments in these regions, the following postmarketing studies were initiated: Study 747-302, a Phase 3b/4 study designed to prospectively obtain evidence to confirm clinical benefit in PBC subjects, and Study 747-401, a Phase 4 study designed to evaluate the pharmacokinetics (PK) and safety of OCA in PBC subjects with hepatic impairment. Both 747-302 and 747-401 terminated early, due to the challenges of recruitment and long-term retention of patients with a rare disease subsequent to Ocaliva regulatory approval. Changes to endpoints and statistical analysis plans to accommodate low recruitment, low events rates, and early termination may necessitate the need for clinical trial data to be supplemented with real-world evidence, with the goal of providing regulators with a more complete evidence package characterizing the efficacy and safety of OCA in patients with PBC.

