7.1.1. Definition of UDCA Failure

UDCA failure includes both inadequate response to UDCA, and intolerance to UDCA. Inadequate UDCA response is defined as:

- At least 1 measure of ALP and/or TB >ULN; and
- \geq 270 days of UDCA treatment prior to ALP and/or TB elevation

UDCA intolerance is defined as:

• A maximum of 90 days of UDCA use with ALP>ULN and/or TB >ULN.

The first date of prescription of OCA after inadequate UDCA response (ALP>upper limit of normal [ULN] and/or total bilirubin [TB]>ULN after >270 days of treatment) or UDCA intolerance (discontinued UDCA after <90 days despite ALP>ULN and/or TB>ULN) will be defined as the index date for OCA-treated PBC patients. The dates of evidence of inadequate UDCA response or UDCA intolerance during which OCA is not utilized will be used as index dates for the non–OCA-treated comparator group.

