As the probabilities used to construct the weights are not known, they will be estimated using a logistic regression model. The model will be fit using observed treatment as the outcome and main effect terms for each of the covariates. Covariates (assessed in the pre-index period) will include:

- Age at index date
- Sex
- Most recent liver biochemistry levels (TB, ALP, ALT, AST)
- Most recent platelet counts
- Time (in months) since UDCA failure
- Clinical evidence of portal hypertension (platelets <150,000 and/or non-bleeding varices)
- Cirrhosis
 - Komodo Health: cirrhosis diagnosis with liver imaging and/or biopsy within 6 months before diagnosis
 - Global PBC registry: biopsy stage 4, transient elastography ≥16.9 kPa, radiological evidence (nodular liver or enlargement of portal vein with splenomegaly), clinical features of portal hypertension defined as platelet count <140 000/mm³ with persistent decrease in serum albumin; or, TB >2x ULN, or prothrombin time/INR > ULN (not due to antithrombotic use)
- Most recent Charlson Comorbidity Index Score (Glasheen 2019)
- Insurance type at the index date (Komodo Health only: commercial, Medicare, Medicaid, dual eligible, other)

All diagnosis, procedure and laboratory codes used to define the control variables are listed in Appendix A.

Once the weights are constructed, a table of weighted SMDs between the groups will be constructed to assess balance. An absolute SMD of greater than 0.1 will indicate potentially problematic residual imbalance for the particular covariate. In the case that either the model-fitting algorithm fails to converge, or residual imbalance exists after weighting, the study team will attempt to reduce model complexity or reduce imbalances by implementing one or more of the following actions:

- Adding/removing interaction terms (1st order or higher)
- Using a spline for continuous variables
- Shrinking all coefficients in the model using a penalty

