10.3. Hypotheses

10.3.1. Primary Hypothesis

These studies are intended to assess whether there is a difference between patients treated with OCA and comparable OCA-eligible patients who are not treated with OCA in the time from index to the first occurrence of all-cause death, liver transplant, or hospitalization for hepatic decompensation.

Two-sided hypotheses are expressed in terms of:

- The null hypotheses (H₀) that the 2 hazard functions are the same, as determined by a hazard ratio (HR) equal to 1; that is, at every timepoint, the instantaneous event rates are the same for the OCA and control populations.
- The alternative hypothesis (H₁) that the 2 hazard rates are not the same ($HR \neq 1$).

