10.4. Determination of Sample Size

Using the sample size in the 2 populations (Section 6.2), the Sponsor computed power to detect treatment effects (relative hazards) of varying sizes, estimated using Cox proportional hazards regression. Computations are based on the formulae of Schoenfeld 1983. To account for confounding control due to the application of IP weights, the Sponsor inflated the variance from the Schoenfeld formula using factors derived by Shook-Sa 2020. It was conservatively assumed just one control observation per patient. In the Komodo Health data, a preliminary investigation found that approximately 395 patients who meet entry criteria will initiate OCA and that 5916 patients will contribute at least one record to the control group (UDCA nonresponders). In the Global PBC registry, the Sponsor expects to have 344 patients meeting entry criteria who initiate OCA, and 2200 who contribute at least one observation to the control group. Power in both cohorts was computed for relative hazards ranging from 0.5 to 0.9 with an alpha level of 0.05. The Sponsor considered baseline event rates during follow-up from 5% to 15% and variance inflation corresponding to mild confounding (VIF=1.05), moderate confounding (VIF=1.5), and strong confounding (VIF=2.0). In each study, power was plotted under these assumptions against a reference line of 80% power under moderate confounding (VIF=1.5) (Figure 2).

Under mild confounding, both studies will be well-powered to detect an HR of 0.5. For moderate confounding, the Komodo Health study will be adequately powered to detect HR of 0.5 for event rates >6%. The Global PBC registry will be adequately powered to detect event rates >8%. Under strong confounding, the Komodo Health study will be adequately powered to detect

HR of 0.5 for event rates >9%. The Global PBC registry will be adequately powered to detect event rates >11%. Power decreases for more moderate HRs. None of the studies under even the most favorable assumptions will be able to detect HRs of 0.9. The Sponsor notes that the assumptions made here are conservative; in particular, it is expected that many more than one control observation and that the addition of lab data from LabCorp (as noted in Section 6.2) will substantially increase the size of both groups in the Komodo Health study.

Figure 2: Power estimates by Hazard Ratio by Level of Confounding for Komodo Health (A) and Global PBC Registry (B).

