10.8. Subgroup Analyses

The entire analysis will be repeated separately by patient race (Komodo Health only), age (categorical), sex, region, absence/presence of cirrhosis, and pre-/post-COVID. Because race is not completely captured in Komodo Health, these analyses will only include those with non-missing values for race.

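### UDCA failure type (inadequate response or intolerance) is needed for eligibility but is not a weight covariate, a balance row or a by-group count; only proxies appear, and Section 10.1.1 and Table 28 disagree on one of them

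*Combined protocol and SAP*

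**What the plan says.** Section 7.1.1 states that "UDCA failure includes both inadequate response to UDCA, and intolerance to UDCA". Inadequate response needs at least 270 days of UDCA before the raised ALP or bilirubin. Intolerance is at most 90 days of UDCA with raised ALP or bilirubin. The index-date paragraph of the same section words intolerance differently: UDCA stopped after fewer than 90 days.

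Section 4.1 links the two routes to different uses of OCA: "in combination with UDCA in adults with an inadequate response to UDCA or as monotherapy in adults unable to tolerate UDCA". In Section 10.1.1 the comparator in the emulated trial is continuation of existing PBC treatment.

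The weight model in Section 10.1.1 is a logistic regression with main effects. Its only UDCA-related covariate is "Time (in months) since UDCA failure". In Appendix B:

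- Tables 1A and 1B count intolerant and inadequate-response patients, overall only.
- Table 21 shows on-UDCA status, yes or no, by group before and after weighting.
- Table 22 is titled "Duration (Months) of Receiving UDCA by Group Before and After" weighting.
- Tables 28 (weight model) and 30 (standardized mean differences) each list UDCA duration.

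Section 10.8 sets the subgroups: "The entire analysis will be repeated separately by patient race (Komodo Health only), age (categorical), sex, region, absence/presence of cirrhosis, and pre-/post-COVID".

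**The concern.** Section 10.1.1 treats as confounders the variables that influence both treatment and outcome. Failure type plausibly does both. A patient who cannot take UDCA faces a different decision about OCA from one already on it, and long UDCA exposure may carry a different prognosis from almost none. The variable has to be derived to apply eligibility, so it is measured. The unmeasured-confounding analysis in Section 10.9 is therefore no substitute for adjusting for it.

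Time since failure records when UDCA failed, not why. A control index on its first failure date has a value near zero by either route. If failure type is out of balance after weighting, intolerant controls can stand in for inadequate responders on OCA, or the reverse, and Table 30 has no row that reports it directly.

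**Working it through.** **1. Where the variable and its proxies appear**

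- Failure type: eligibility (7.1.1) and overall counts (Tables 1A, 1B). Absent from the 10.1.1 covariates, Tables 16 to 30 and the 10.8 subgroups.
- On-UDCA status: Table 21 by group. Absent from 10.1.1 and from Tables 28 and 30.
- UDCA duration: Tables 22, 28 and 30. Absent from 10.1.1.

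Section 10.1.1 and Table 28 therefore specify different weight models with respect to duration.

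**2. Would a duration term balance failure type?**

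The routes are at most 90 versus at least 270 days, so duration nearly identifies the type. A main effect, however, models treatment odds as log-linear in months, while the two routes differ by a step. This was checked in a simulation of 200,000 indices. All inputs are assumed: 10% intolerant; duration uniform over 0 to 3 months if intolerant, otherwise 9 months plus an exponential with mean 36; odds ratio 3 between intolerance and OCA initiation; no other covariates. The SMD of failure type was:

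- unweighted: 0.38 (23.0% of OCA, 9.2% of control indices intolerant);
- SMR weights with linear duration: 0.32 (controls 11.1%);
- SMR weights with linear, squared and log duration: 0.04;
- SMR weights with a failure-type indicator: 0.00.

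With an odds ratio of 1/3 the four values were -0.27, -0.25, -0.05 and 0.00. In both cases the linear term left an absolute SMD above the plan's flag of 0.1.

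**3. Possible size**

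The plan gives no figure for the split by failure type, so there is none to reproduce. The Section 10.9 formula is

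factor = (OR × P1 + 1 − P1) / (OR × P0 + 1 − P0),

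where P1 and P0 are the intolerant shares among OCA and control indices and OR is the association of intolerance with the outcome. With assumed OR 1.5 and then 2.0:

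- P1 10%, P0 20%: 1.05/1.10 = 0.955; 1.10/1.20 = 0.917.
- P1 10%, P0 30%: 1.05/1.15 = 0.913; 1.10/1.30 = 0.846.
- P1 20%, P0 10%: 1.10/1.05 = 1.048; 1.20/1.10 = 1.091.
- P1 30%, P0 10%: 1.15/1.05 = 1.095; 1.30/1.10 = 1.182.
- P1 = P0: 1.00.

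A wider assumed grid, 5% to 20% in each group and OR 1.5 to 3, runs from 0.79 to 1.27. A small imbalance is enough to cross the flag: for 10% versus 5%, SMD = 0.05/√[(0.10×0.90 + 0.05×0.95)/2] = 0.05/0.262 = 0.19.

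**4. What a restricted sensitivity analysis would cost in power**

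Section 10.4 says: "Power in both cohorts was computed for relative hazards ranging from 0.5 to 0.9 with an alpha level of 0.05"; the hypotheses in 10.3.1 are two-sided. Schoenfeld power is Φ(|ln HR|·√[D·p(1−p)] − 1.96), with D = total N × event rate / VIF and p the OCA share. At HR 0.5 and the plan's thresholds this gives 76.0% for Komodo (6%, VIF 1.5), 80.8% for Komodo (9%, VIF 2.0), 78.8% for Global PBC (8%, VIF 1.5) and 80.1% for Global PBC (11%, VIF 2.0). That is close to the plan's 80% statements; Komodo at VIF 1.5 reaches 80% at 6.6%.

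Now assume 5% to 20% intolerant in each group, a 10% event rate, VIF 1.5 and HR 0.5. With 20% removed:

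- Komodo: D = 6311 × 0.8 × 0.10/1.5 = 336.6 and p = 395/6311 = 0.0626, so power is 86.9%.
- Global PBC: D = 2544 × 0.8 × 0.10/1.5 = 135.7 and p = 344/2544 = 0.135, so power is 78.8%.

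Over 5% to 20%, inadequate responders alone keep 87% to 92% (Komodo) and 79% to 85% (Global PBC). The intolerant stratum would hold about 20 to 79 and 17 to 69 OCA patients, with power of 12% to 34% and 10% to 28%.

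**The case against.** A reader might infer that two populations are pooled with no adjustment and that no table would reveal it. The documents do not support that. Tables 21 and 22 show close proxies by group before and after weighting, and Tables 28 and 30 put duration in the weight model and the balance check. Section 10.1.1 allows splines and interactions when balance fails, and flexible duration terms brought the SMD to 0.04 in the simulation. This stands, but it is partial cover. Duration is not in the 10.1.1 list. Splines are a fallback, used on non-convergence or imbalance in a covariate that is checked, and failure type is not checked. Table 21 has no row in Tables 28 or 30, and Table 22 gives summary statistics rather than the share at or below 90 days.

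A reader might also infer that the hazard ratio mixes two different effects. Section 4.4 points the other way: it reports consistent Phase 2 efficacy as monotherapy and as add-on. Those are three-month studies of ALP and other biochemical markers, not clinical events, but nothing in the documents shows heterogeneity. An average effect among the treated, over a population within the indication, is a legitimate estimand.

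Nor is failure type uniquely fixed at every index. Section 7.1.1 words intolerance two ways, and a patient who resumes UDCA could meet one route early and the other later.

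Finally, nothing in the documents shows that failure type still matters once liver biochemistry, platelets, cirrhosis and time since failure are weighted. That is so; the case for confounding is one of plausibility.

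**Conclusion.** The point holds as a gap in specification. A baseline variable that the plan must derive, and that plausibly bears on both treatment and prognosis, is not in the weight model, the balance table or any by-group count. The proxy that comes closest is in the shells but not in the Section 10.1.1 list, and as a main effect it need not balance failure type.

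It does not show that the primary estimate is biased. The factors of 0.85 to 0.96, or 1.05 to 1.18 with the splits reversed, rest wholly on assumed shares and on intolerance raising risk by an odds ratio of 1.5 to 2.0. They also assume that the other covariates absorb none of the imbalance. If intolerance lowered risk, the directions would swap. This is an inexpensive improvement to make before the weights are final.

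**What to change.** - Section 7.1.1: reconcile the two wordings of intolerance, and state how type is assigned when an index could meet both routes.
- Sections 10.1.1 and 10.2: add a failure-type indicator at index to the weight covariates and the Cox covariates.
- Tables 28 and 30: add a row for failure type. Add a table of its counts by group before and after weighting.
- Reconcile UDCA duration between Section 10.1.1 and Tables 28 and 30. If it is kept, state its functional form.
- Optional: a sensitivity analysis restricted to inadequate responders. A separate intolerant subgroup would probably be too small to inform.

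The cost is one binary covariate built from data already used for eligibility, one row in each of two shells and one short table. The downside is one more parameter and a possibly sparse cell of intolerant OCA patients. Section 10.1.2 keeps outcomes blinded until the weights are final, so the change should be made before then.
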